## 5.3 Rescreening

Subjects who are screen failures (Section 5.4) may be rescreened with approval from the Medical Monitor. Rescreened subjects should be assigned a new subject number different from the initial screening event.

Rescreening due to failure to meet the following Inclusion Criteria is not allowed for Inclusion Criteria # 5, 6, 7, or 8.

## 5.4 Screen Failures

Screen failures are defined as subjects who consent to participate in the clinical study but did not receive study medication. See Section 7.1.1 for instructions on managing subjects who did not meet the eligibility criteria but received study medication in error.

A minimal set of screen failure information is required to ensure transparent reporting of screen failure subjects to meet the Consolidated Standards of Reporting Trials publishing requirements and to respond to queries from regulatory authorities. Minimal information includes demography, screen failure details, eligibility criteria, and any SAEs.

## 6.0 STUDY TREATMENT

Subjects will receive ensifentrine administered using the inhaled route via a standard jet nebulizer supplied by the Sponsor.

In this protocol the terms 'investigational product,' and 'study medication' are the same and refer to the nebulized ensifentrine (3 mg) or OHTUVAYRE.

## 6.1 Dispensing of Medical Devices

Subjects will be dispensed study supplied medical devices as per the schedule outlined in the Schedule of Activities (SoA) (Table 1).

No Sponsor manufactured medical device is used in this study.

Each eligible subject will be dispensed a study supplied nebulizer, with a compressor:

- PARI LC ®Sprint nebulizer
- PARI PRONEB ®Max Aerosol Delivery System or equivalent

At Visit 3, a new PARI LC Sprint® nebulizer will be supplied, if needed. Instructions for medical device use are provided in the package insert.

The study medication should only be administered with the study provided nebulizer. No medications other than the study medication should be administered with the study provided nebulizer.

## 6.2 Dispensing of Study Medication

Subjects will be dispensed study medication kit(s) as per the schedule outlined in the Schedule of Activities (SoA) (Table 1).

## 6.3 Administration of Study Medication

Study medication will be administered by inhalation of an aerosol generated by the study supplied reusable nebulizer attached to the compressor.

## 6.3.1 Dosing in the Clinic

At Visit 2, the first dose of study medication will be administered in-clinic with the study supplied nebulizer and compressor.

- Following informed consent and eligibility confirmation, study medication will be administered by inhalation of an aerosol generated by the reusable study supplied nebulizer attached to a study supplied compressor.
- The site staff member will need to follow the nebulizer Set-Up instructions provided with the nebulizer and the Pharmacy Manual to prepare and administer study medication.

- Administration of nebulized study medication will be observed by the site staff member from start of nebulization until end time of nebulization. The site staff member MUST administer and observe study medication.
- Study medication nebulization time should be approximately 5 to 10 minutes.
- The end time of study medication nebulization is when a slight sputtering sound from the nebulizer is heard.
- The date, the start time, and the end time of study medication nebulization will be recorded by the site staff member in the subject source document and the electronic case report form (eCRF).

### 6.3.2 Dosing at Home

Subjects will take their study supplied nebulizer and compressor as well as instructions home for use during the study.

Following Visit 2, subjects will self-administer their daily morning and evening doses of study medication at home at approximately the same times each day, approximately 12 hours apart, for 12 weeks.

- Prior to dosing at home, subjects must take their background maintenance COPD medication approximately 2 minutes prior to taking study medication.
- The morning doses of COPD maintenance medication and study medication must be taken at home in the morning prior to Visit 3 and Visit 4.
- Each subject will follow the Nebulizer Set-Up instructions and study medication label to prepare and self-administer the study medication by inhalation using the reusable study supplied nebulizer attached to the study supplied compressor.
- Study medication nebulization time should be approximately 5 to 10 minutes; until a slight sputtering sound from the nebulizer is heard.

Subjects will be instructed as follows:

- Only a study supplied nebulizer and compressor may be used to administer study medication. Only study medication may be used in the study supplied nebulizer and compressor.
- Discard used study medication ampules and open foil pouches of used study medication at home.
- Return unused study medication ampules to the clinic at Visit 3 and Visit 4 for collection, and assessment of medication compliance by a site staff member (Section 6.6).

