## **1.3** Schedule of Activities

### Table 1: Schedule of Assessments and Procedures

	Study Start	Treatment Period		rt Treatment Period Study		Study End	Early Wit Termin	hdrawal / nation ¥
	Screening	Day 1 (≤7 days)	Week 6 (42 ± 3 days)	Week 12 (42 ± 3 days)	7 ± 3 days after Visit 4	As Soon as Possible after EW/T	7 ± 3 days after EW/T Visit	
	Visit 1	Visit 2	Visit 3	Visit 4 (EOT)	Follow-up	EW/T Visit	Follow-Up	
Informed consent A	X							
Inclusion/exclusion criteria (eligibility review)	X	Review, Update						
Demographics (date of birth, age, gender, race, ethnicity)	X							
CAT ™ training	X							
CAT TMB	X*		X*	X*				
mMRC (administered by study team)	X							
Medical, surgical, smoking history	X	Review, Update						
Prior and concomitant medication	X							
Vital signs (blood pressure and pulse rate)		Х	Х	X		Х		
Height and Weight; BMI calculated		Х						
Brief physical exam C		Х						
Urine pregnancy test D		Х	X	X				
Pre- and post-bronchodilator Spirometry E		Х						
Nebulizer equipment materials dispensing, review, and training; collection at end F		Х	X	Х		X		
Study medication dispensing G		Х	X					
In clinic study medication dosing		Х						
Concomitant medication review		Х	X	X	X	X	Х	
Study medication compliance			X	X		X		
AE and SAE recording		Х	X	X	Х	X	X	
Phone call to subject					Х		Х	

**Note**: Information and details on most of the Study Assessments and Procedures can be found in Section 8.0. \*The CATTM is completed by the subject on paper first before any procedures and assessments. ¥The early withdrawal / termination visit should be conducted as soon as possible. If possible, subjects should remain on study medication through the early termination visit (Section 7.2).

- A. Informed consent must be obtained by the process described in Appendix 2. Consent must be obtained prior to any study procedures being performed.
- B. Following informed consent, the CATTM is performed first before any procedures and assessments.
- C. Assessments of the Cardiovascular, Respiratory, Gastrointestinal, and Neurological systems.
- D. Pregnancy Testing: Pregnancy testing will be conducted on women of childbearing potential only (refer to Appendix 4).

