The CAT will be completed on paper at Visits 1, 3 and 4 prior to any study procedures to avoid influencing the subject's response. All questions must be answered. Answers to each question will be logged into the eCRF by the study team.

A follow-up phone call will be made to the subject approximately one week after the end of treatment.

Subjects may remain on prescribed short- and long-acting COPD medications throughout participation provided they are not included in the prohibited medication list. COPD exacerbations should be treated at physician's discretion as per usual practice.

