## 5.1 Inclusion Criteria

- 1. Capable of giving informed consent indicating that they understand the purpose of the study and study procedures and agree to comply with the requirements and restrictions listed in the ICF and in this protocol.
- 2. Aged 40 to 80 years of age inclusive, at the time of screening.
- 3. Sex:
  - Males are eligible to participate if they agree to use contraception as described in the contraceptive guidance (Appendix 4) from screening and throughout the study and for at least 30 days after the last dose of study medication.
  - Females are eligible to participate if they are not pregnant, not breastfeeding, and  $\geq 1$  of the following conditions apply:
    - a) Not a woman of childbearing potential (WOCBP) as defined in Appendix 4.
      - OR
    - b) A WOCBP who agrees to follow the contraceptive guidance in Appendix 4 from screening and throughout the study and for at least 30 days after the last dose of study medication.
- 4. Current or former cigarette smoker with a history of cigarette smoking ≥ 10 pack years. Note: Pipe and/or cigar use cannot be used to calculate pack-year history. Former smokers are defined as those who have stopped smoking at least 6 months prior to screening. Smoking cessation programs are permitted during the study.
- An established clinical history of COPD as defined by the American Thoracic Society (ATS)/European Respiratory Society (ERS) guidelines with symptoms compatible with COPD.
- 6. Pre- and post-bronchodilator (4 puffs of albuterol) spirometry at Visit 2 demonstrating the following:
  - Pre- and post-albuterol  $FEV_1$ /forced vital capacity (FVC) ratio of < 0.70.
  - Post-albuterol  $FEV_1 \ge 30$  % and  $\le 75$ % of predicted normal.
- 7. A score of  $\geq 2$  on the modified Medical Research Council Dyspnea Scale at Visit 1.
- 8. A score of  $\geq 10$  on the COPD Assessment TestTM at Visit 1.
- 9. Demonstrates stable use of dual (LAMA+LABA) or triple (LAMA+LABA+ICS) maintenance therapy, in any form (except nebulized) for at least 8 weeks prior to screening and agrees to continue use for the duration of the study. *Note: The*

number taking LAMA+LABA+ICS will be capped at ten (10). The use of LAMA or LABA alone or with ICS is not permitted (e.g., LABA+ICS, LAMA).

- 10. Capable of withholding short-acting rescue medications for 4 hours, Twice-Daily maintenance therapy for 24 hours or Once-Daily maintenance therapy for 48 hours prior to Visit 2.

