## 8.1.1.3 COPD Assessment Test (CATTM)

Site staff will review the CAT form and provide instructions to the subject. The CAT will be completed on paper by the subject per the instructions in Section 8.2. The completed CAT will be logged into the eCRF by the study team.

• The order should be CAT followed by the mMRC.

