## 8.2 Efficacy Assessment

Planned timepoints for all efficacy assessments are provided in the SoA (Table 1).

The CAT™ is a one-page, 8-item questionnaire suitable for completion by patients diagnosed with COPD. When completing the questionnaire, individuals rate their experience on a 6-point scale, ranging from 0 (no impairment) to 5 (maximum impairment) with a scoring range of 0-40. Higher scores indicate greater disease impact. Refer to Appendix 5.

The CAT will be completed on paper and must be the first assessment completed at Visits 1, 3 and 4 to avoid influencing the subject's response. At Visit 1, the order should be CAT followed by the mMRC.

All questions must be answered, and the subject should not be told their results. It is recommended that the questionnaire be administered at the same time of day at each visit. Answers to each question will be logged into the eCRF by the study team.

Adequate time must be allowed to complete all items on the questionnaire; the questionnaire must be reviewed for completeness and, if necessary, the subject should be encouraged to complete any missing items.

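### Baseline and follow-up CATs are not standardised for time since the last maintenance dose, which in a single-arm study could inflate the Week 12 responder proportion

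*Protocol*

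**What the plan says.** **Follow-up CATs.** Protocol Section 6.3.2 (Dosing at Home) states that the morning doses of maintenance and study medication "must be taken at home in the morning prior to Visit 3 and Visit 4". Section 8.2 adds that the CAT "must be the first assessment completed at Visits 1, 3 and 4 to avoid influencing the subject's response". Together these make the Week 6 and Week 12 CATs post-dose by rule, although the interval in hours is not fixed.

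**Baseline CAT.** Section 4.1 gives the schedule: "The CAT will be completed on paper at Visits 1, 3 and 4 prior to any study procedures". There is no CAT at Visit 2, so Visit 1 supplies the only pre-treatment score. Section 8.1.1.3 refers to Section 8.2 for how it is done. Section 8.2 covers order, completeness and, as advice only, time of day: "It is recommended that the questionnaire be administered at the same time of day at each visit". Inclusion criterion 9 requires stable dual or triple therapy for at least 8 weeks before screening. No section says how long before the Visit 1 CAT the last maintenance dose should have been taken.

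**The hold.** Inclusion criterion 10 requires that subjects can withhold "Twice-Daily maintenance therapy for 24 hours or Once-Daily maintenance therapy for 48 hours prior to Visit 2". Table 4 repeats these times for Visit 2 spirometry and has maintenance resume after that visit. Table 1 places Visit 2 at most 7 days after Visit 1 and gives no minimum gap.

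**The concern.** The study asks what ensifentrine adds to unchanged standard of care. That needs the maintenance inhaler to be in a comparable state at baseline and at follow-up. The plan fixes that state at follow-up only. A subject who comes to Visit 1 before the morning inhaler gives an end-of-interval baseline, which is then compared with a post-dose score at Weeks 6 and 12. The reverse mismatch cannot occur if the plan is followed, so any effect would tend to go one way, towards apparent improvement.

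With no control arm, such a difference cannot be separated from the drug effect. A responder needs only a 2-point improvement, so a modest shift can change a subject's classification. The same Visit 1 score also decides eligibility (CAT of at least 10), so a score raised by dose timing could both admit a subject and set that subject's baseline.

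The data as planned would not reveal it. Section 6.7.3 records maintenance by start date, dose and frequency, with the end date entered as ongoing. No section asks for the time of the last dose at a CAT.

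**Working it through.** **1. The plan's own figure.** SAP Section 5 assumes 30% of 20 subjects, or 6 responders, with standard error √6. The interval is 6 ± 1.96 × √6 = (1.199, 10.801), as stated.

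**2. Can the baseline CAT fall inside the hold?** Hold start relative to Visit 1 = gap between visits − hold length. A negative value means the hold has begun before the baseline CAT.

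| Visit 1 to 2 gap | Twice-daily user (24 h hold) | Once-daily user (48 h hold) |
|---|---|---|
| Same day | −24 h | −48 h |
| 1 day | 0 h | −24 h |
| 2 days | +24 h | 0 h |
| 7 days | +144 h | +120 h |

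Overlap needs a gap under 24 h (twice daily) or under 48 h (once daily). The two short gaps differ in kind:
- Same-day visits mean a dose was withheld before consent.
- A next-day Visit 2 does not require that. A once-daily user who doses at 9:00 on day 0, completes the CAT at 9:00 on day 1 before dosing, and attends Visit 2 at 9:00 on day 2 meets the 48 h rule. The baseline CAT is then 24 h after the last dose, the end of an ordinary once-daily interval.

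With longer gaps there is no overlap, but an end-of-interval baseline remains possible because time since dose is not specified.

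**3. How sensitive is the responder proportion?** Take the change in CAT as normal with the plan's SD of 4.5. P(responder) = P(change ≤ −2) = Φ((−2 − mean)/4.5). With no drug effect:
- no shift: Φ(−2/4.5) = 32.8%
- assumed 1-point shift: Φ(−1/4.5) = 41.2%
- assumed 2-point shift: Φ(0) = 50.0%

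With an integer-score cut at −1.5 these become 36.9%, 45.6% and 54.4%. All apply within affected subjects only.

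**4. Averaged over the study.** Start from the planned 30%, which with SD 4.5 corresponds to a mean change of +0.36. Let a fraction f of subjects have a baseline shift d. Then P = (1 − f) × 30% + f × Φ((−2 − 0.36 + d)/4.5). For d = 1 and f = 25%: 0.75 × 30% + 0.25 × 38.1% = 32.0%.

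| Shift d (assumed) | f = 25% | f = 50% | f = 100% |
|---|---|---|---|
| 0.5 | 31.0% | 32.0% | 34.0% |
| 1 | 32.0% | 34.1% | 38.1% |
| 2 | 34.2% | 38.4% | 46.8% |

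Expected responders move from 6.0 to between 6.2 and 9.4 of 20. The documents give neither d nor f.

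**5. Effect on the success call.** SAP Section 8.4.5.1 requires a lower confidence limit above 0. Under the sample-size approximation, 3 responders give 3 − 1.96 × √3 = −0.39 and 4 give 4 − 1.96 × √4 = +0.08, so 4 of 20 suffice. The chance of at least 4 is 89.3% at a 30% rate and 92.4% at 32.0%.

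**The case against.** **The hold belongs to Visit 2, not Visit 1.** The baseline CAT comes straight after consent, and Table 1 says "Consent must be obtained prior to any study procedures being performed". A subject who begins the hold after consenting has already completed the CAT. The plan also treats the visits as separate. Participation of about 14 weeks, less 12 weeks of treatment and about 1 week of follow-up, leaves about 1 week for screening. This stands. A reader might infer that baseline is routinely taken off maintenance, so that resuming the inhaler is counted as response. The documents do not support that. Overlap beyond an ordinary dosing interval is an edge case that no section plans, though none excludes it.

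**Being on maintenance is the default.** Eight weeks of stable use is required, and the recommended common time of day partly aligns the CATs. This also stands, but it governs the regimen and the clock. Neither settles whether that morning's dose had been taken, which Section 6.3.2 does settle for Visits 3 and 4.

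**Rescue use.** A reader might add untimed rescue medication as a second source of inflation. It is as needed and untimed at all three CATs, so it is not a baseline-versus-follow-up difference. It is at most a recording gap.

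**No evidence of size.** No section says that a late or missed inhaler dose moves the CAT, which includes items such as sleep, confidence and energy. A 2-point shift would equal the responder threshold itself. The illustrations show sensitivity and do not establish that inflation occurs.

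**Conclusion.** The mismatch is real. Follow-up CATs are tied to a morning maintenance dose and the baseline CAT is not, and the schedule does not keep the baseline clear of the end of a dosing interval or, in the same-day edge case, of the Visit 2 hold. In a single-arm study, any CAT difference that results would be attributed to ensifentrine and could raise the Week 12 responder proportion and the mean improvement.

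The size cannot be stated. It rests on two quantities missing from the documents, the CAT shift and the share of subjects affected, and on a normal change with SD 4.5. A 1-point shift in a quarter of subjects adds about 2 percentage points to the planned 30%; larger figures need a larger shift or a larger share.

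It would be wrong to read this as undermining the success criterion. That criterion is easily met with or without a shift. The issue matters because Protocol Section 9.1 sets the aim as quantifying response. Severity is minor to moderate, and correcting it is a cheap improvement.

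**What to change.** 1. Reconcile Table 1, inclusion criterion 10, Section 6.3.2, Table 4 and Section 8.2 so that baseline and follow-up CATs are measured under comparable maintenance-timing conditions and the baseline CAT is scheduled outside the Visit 2 hold. This concerns when the questionnaire is given; no dose or withholding rule needs to change.
2. Record the time of the last maintenance dose with each CAT in the eCRF and, as a recording item only, the time of last rescue use.
3. Add to SAP Section 8.4.5.3 a sensitivity analysis of the Week 12 responder proportion that leaves out subjects whose baseline CAT fell within the hold. For subjects already enrolled, use a Visit 1 to 2 gap under 24 h for twice-daily or under 48 h for once-daily maintenance. This will not find end-of-interval baselines with longer gaps; only the new time field can do that.

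Cost: a small scheduling constraint, one or two eCRF fields, and one extra run on possibly slightly fewer than 20 subjects. If no subject is affected, reporting that count closes the hold question.

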## 6.4 Investigational Product/ Study Medication

Investigational product/study medication is described in Table 2.
#### **Table 2: Investigational Product/Study Medication Details**

The ensifentrine formulation

, and supplied

as a 2.5 mL nominal fill in single unit-dose low density polyethylene (LDPE) translucent ampule overwrapped in a foil pouch.

Ensifentrine is manufactured using aseptic manufacturing techniques in accordance with Good Manufacturing Practice guidelines and will be provided to the site as subject kits to be dispensed at Visit 2 and Visit 3.

## 6.4.1 Study Medication Formulation Information

The study medication formulation constituent and concentrations are described in Table 3.

## 6.5 Preparation/Handling/Storage/Accountability

Study medication should be stored below 25°C (77°F) at controlled room temperature and should not be frozen.

An investigator or designee must confirm appropriate temperature conditions have been maintained during transit for all study medication received and any discrepancies are reported and resolved before use of the study medication.

All study medication must be stored in a secure, environmentally controlled, limited access, monitored (manual or automated) area in accordance with the labeled storage conditions with access limited to the Investigator and authorized study center staff.

#### Protocol RPL554-CO-303

The temperature should be monitored, and logs maintained in areas where study medication is stored. If temperature conditions have been compromised or any study medication has not been stored appropriately, this should be documented, and the study medication quarantined until the Sponsor has been notified and confirmed whether it may be used.

Only subjects meeting the eligibility criteria in the study may receive study medication and only authorized study center staff may supply or administer study medication.

The Investigator, institution, or the head of the medical institution (where applicable) is responsible for study medication accountability, reconciliation, and record maintenance (i.e., receipt, reconciliation, and final disposition records).

Further guidance and information for the final disposition of unused study medication are provided in the Pharmacy Manual.

The Investigator, a member of the study center staff, the site pharmacist, or pharmacy team member must maintain an adequate record of the receipt and distribution of all study medication using the Drug Accountability Form. These forms must be available for inspection at any time.

## 6.6 Study Medication Compliance

The prescribed dosage, timing, and mode of administration may not be changed. Any departures from the intended regimen must be recorded in the eCRFs.

At Visit 3 (Week 6), prior to dispensing study medication, previously dispensed/unused study medication will be retrieved, and compliance assessed by the site staff member. Subjects exhibiting poor compliance, as assessed by the number of ampule/foil pouch counts dispensed and returned, should be counseled on the importance of good compliance to the study dosing regimen and this counseling should be documented in the subject source document.

At Visit 4 (Week 12), previously dispensed/unused study medication will be retrieved, and compliance assessed by the site staff member.

Non-compliance is defined as taking less than 70% of study medication during any evaluation period (visit to visit).

